#### 7.1.5 Analysis of the outcome measures for the ancillary studies

- ANCILLARY STUDY 1

- Analysis of the primary outcome measure

Plasma citrulline levels at H72 will be analyzed using the approach described for the calorie intake.

- Analysis of the secondary outcome measures
- SOFA score: SOFA score changes over time will be evaluated graphically by placing daily boxplots on the same graph. For between-group comparisons of SOFA score changes over time, a mixed linear model will be built, after transformation of the data if needed.
- Plasma citrulline and I-FABP levels at D0, D3, and D8: the changes in these variables over time will be evaluated graphically by placing daily boxplots on the same graph. For between-group comparisons, a mixed linear model will be built, after transformation of the data if needed.
- Proportion of patients whose plasma I-FABP is  $\geq 100$  pg/mL on D0, D3, and D8: the analysis method will be the same as for the primary NUTRIREA2 outcome measure.
- Proportion of patients whose plasma citrulline is  $\leq 10$   $\mu$ L/L on D0, D3, and D8: the analysis method will be the same as for the primary NUTRIREA2 outcome measure.
- Proportion of patients with at least one episode of bacteremia: the analysis method will be the same as for the primary NUTRIREA2 outcome measure.
- Proportion of patients with at least one episode of gastrointestinal intolerance: the analysis method will be the same as for the primary NUTRIREA2 outcome measure.
- Proportion of patients with at least one episode of diarrhea: the analysis method will be the same as for the primary NUTRIREA2 outcome measure.
- ANCILLARY STUDY 2
  - Analysis of the primary outcome measure

The chi-square test will be applied to compare the proportion of patients with abundant microaspiration in the two groups. The odds ratio with its 95% confidence interval will be computed.

  - Analysis of the secondary outcome measures

Patient characteristics in the two groups will be compared. Qualitative variables will be compared using either the chi-square test or Fisher's exact test. Shapiro-Wilk's test will be applied to determine whether the quantitative variables are normally distributed. These quantitative variables will then be compared using Student's *t* test if normally distributed and the Mann-Whitney U test otherwise.

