#### 4.2.4 Study intervention: first-line enteral or parenteral nutrition

After study inclusion, patients will be allocated at random to one of two nutritional-support strategies (Figure 1).

[figure not shown]
**In the parenteral-nutrition group (P group),** the patients will receive first-line parenteral nutrition for at least 72 hours. After these 72 hours, the course of action will depend on the results of the daily hemodynamic status evaluation. If the hemodynamic condition is stable (no vasoactive amines for 24 consecutive hours and arterial lactic acid level below 2 mmol/L) and the enteral route can be used, parenteral nutrition will be stopped and immediately replaced by enteral nutrition at the flow rate needed to achieve the previously defined calorie target. If on the contrary the patient still requires vasoactive amine therapy and/or the arterial lactic acid level is equal to or greater than 2 mmol/L, parenteral nutrition will be continued for a total of 7 days (168 hours). On day 8, in the absence of contraindications to enteral nutrition, parenteral nutrition will be stopped and enteral nutrition started. Supplemental parenteral nutrition may be added subsequently in the event of intolerance to enteral nutrition precluding the achievement of the predefined calorie targets.

**In the enteral-nutrition group (E group),** the patients will receive first-line enteral nutrition. In the event of persistent gastrointestinal intolerance precluding achievement of the

---

predefined calorie targets, supplemental parenteral nutrition may be added starting on day 8 in compliance with North-American recommendations and with the recently published study by Casaer (6, 72). Isoosmotic isocaloric normal-protein polymeric preparations will be used during the first week, after which the choice of the preparation will be at the discretion of the physician. To minimize the risk of gastric intolerance and consequently of vomiting, the volume of supplemental water given enterally will be as small as possible during the first study week.

Figure 1: Protocol

---

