- The number of calories delivered each day by the enteral and parenteral routes: changes over time in delivered calories will be represented graphically by boxplots created each day on the same graph; changes over time will be compared between the two groups using a mixed linear model, after data transformation if necessary
- Volume of enteral and parenteral feeds delivered each day: the analysis method will be the same as for the number of calories
- Ratio of prescribed over delivered calories: the proportions of patients who achieved their daily calorie target will be determined at each follow-up time point (in days) and will be compared between the two groups using a logistic random effects model
- ICU mortality, 90-day mortality, and hospital mortality: day-90 mortality will be analyzed in the same way as day-28 mortality; for ICU and hospital mortality rates, competing-risk models will be used, as ICU discharge and hospital discharge compete with death during the stay
- Nutritional markers and body weight: changes over time in nutritional markers and body weight will be analyzed using the method described above for the number of calories delivered
- Proportion of patients with at least one episode of liver dysfunction: the method will be the same as for the primary objective
- Times in the ICU, in the hospital, and on mechanical ventilation will be compared between the two groups using nonparametric Wilcoxon tests

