### Ancillary studies

#### *– Ancillary study 1*

The primary outcome measure is the plasma citrulline level at H72. To demonstrate a significant difference between plasma citrulline levels of 16  $\mu\text{moL/L}$  (enteral-nutrition group) and 12  $\mu\text{moL/L}$  (parenteral-nutrition group), with a standard deviation of 8  $\mu\text{moL/L}$ , a two-tailed test, the alpha risk set at 0.05, and 90% power, 85 patients will be needed in each group (170 patients in all).

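### Ancillary study 1 is sized on the citrulline difference at H72, but its primary analysis is referred to a change-over-time mixed model that does not name that contrast, so the 90% power is not assured

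*Combined protocol and SAP*

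**What the plan says.** Section 7.2 (Ancillary study 1) fixes the endpoint, "The primary outcome measure is the plasma citrulline level at H72", and sizes the study on expected levels of 16 µmol/L (enteral) and 12 µmol/L (parenteral) with SD 8: "a two-tailed test, the alpha risk set at 0.05, and 90% power, 85 patients will be needed in each group". Sections 5.11 and 4.1.3 name the same single time point.

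For the primary analysis, 7.1.5 says only: "Plasma citrulline levels at H72 will be analyzed using the approach described for the calorie intake". The calorie-intake entry in 7.1.4 consists of daily boxplots and a model in which "changes over time will be compared between the two groups using a mixed linear model, after data transformation if necessary". Section 7.1.5 then gives boxplots and a mixed linear model again, as the secondary analysis of citrulline at D0, D3 and D8.

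No section states an H72 contrast, the coding of time, the handling of the D0 value, a covariance structure or a within-patient correlation.

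**The concern.** The study asks whether citrulline differs between groups at H72, and 85 per group answers that question. The method cited for the primary analysis asks whether the groups' courses over time differ. That can be tested in several ways, and the plan does not say which one is primary. Because the secondary analysis of the same marker uses the same type of model, nothing separates the two. For ancillary study 2, by contrast, 7.1.5 names the chi-square test and the odds ratio.

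The D8 sample makes the choice matter. Under 4.2.4, parenteral patients may move to the enteral route after 72 hours once stable, and for those still on parenteral feeding: "On day 8, in the absence of contraindications to enteral nutrition, parenteral nutrition will be stopped and enteral nutrition started". An effect that spans D0, D3 and D8 therefore combines the intended comparison with a visit at or after the time when the feeding routes converge.

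At stake is whether the stated power belongs to the test that will be reported, and whether that test is fixed before the data are seen. Section 7.6 finalizes the analysis plan only at database lock, in an open-label trial.

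**Working it through.** **Inputs from the documents.** Difference at H72: 16 − 12 = 4. SD 8. Two-sided alpha 0.05. 85 per group. Samples on D0, D3 and D8 (4.2.7 and 4.6). No separate H72 draw is listed, so the D3 sample is taken as the H72 value.

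**Assumptions, because the documents give no figure.** Within-patient correlation ρ = 0.3, 0.5 or 0.7, equal between all visits; SD 8 at every visit; no group difference at D0; group difference at D8 of 0, 2 or 4; complete data, except in the last step.

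**1. The plan's own figure.** n = 2 × [8 × (1.960 + 1.282)/4]² = 84.06, rounded up to 85 per group. Power at 85 is 90.3% by the normal approximation and 90.0% by the t distribution. The stated 85 is right for a two-sample comparison at H72.

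**2. H72 contrast, alone or inside a mixed model with categorical time.** SE = 8 × √(2/85) = 1.227; 4/1.227 = 3.26; power 90.3% at any ρ.

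**3. Group difference in D0-to-D3 change.** SD of change = 8 × √(2(1 − ρ)) = 9.47, 8.00, 6.20. Standardized effects 2.75, 3.26, 4.21.

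**4. Group-by-time interaction, 2 df.** Noncentrality = (85/2) × Σ(d − mean d)² / [64(1 − ρ)], where d are the group differences at D0, D3 and D8. For (0, 4, 2) the sum of squares is 8, giving noncentrality 7.59, 10.63, 17.71. For (0, 4, 0) and (0, 4, 4) it is 10.67, giving 10.12, 14.17, 23.61.

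**5. Linear slope, if time were coded that way.** With times 0, 3 and 8 the mean is 3.67, Σ(t − mean)² = 32.67, and the weights are −0.1122, −0.0204 and 0.1327. SE = √[64(1 − ρ)(2/85)/32.67] = 0.180, 0.152, 0.118. The slope difference is 0.184 per day for (0, 4, 2) and 0.449 per day for (0, 4, 4).

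**6. H72 comparison adjusted for D0.** SD = 8 × √(1 − ρ²) = 7.63, 6.93, 5.71.

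| Effect tested (85 per group) | ρ = 0.3 | ρ = 0.5 | ρ = 0.7 |
|---|---|---|---|
| H72 contrast | 90% | 90% | 90% |
| D0-to-D3 change | 79% | 90% | 99% |
| Interaction, D8 difference 2 | 69% | 84% | 97% |
| Interaction, D8 difference 0 or 4 | 82% | 93% | 99.5% |
| Linear slope, D8 difference 2 | 17% | 23% | 35% |
| Linear slope, D8 difference 4 | 71% | 84% | 97% |
| H72 adjusted for D0 | 92% | 96% | 99.5% |

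**7. Missing H72 samples.** Section 7.2 states no allowance. Under an assumed loss of 10% (85 × 0.90, taken as 76) or 15% (85 × 0.85, taken as 72), unadjusted power by the t distribution is about 86% or 85%.

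**The case against.** The strongest reply is that 7.1.5 speaks of levels at H72 and lists the D0/D3/D8 course separately. On that reading H72 is the target and the fault is a loose cross-reference. A mixed model with categorical time can deliver the H72 contrast with the planned power. This stands in part: H72 may well be what was meant. It does not remove the gap, because the method cited compares changes over time and nothing tells the analyst to take the H72 contrast from it.

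Two stronger readings are tempting, and the documents support neither.

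- A reader might infer that the planned analysis fails to reach 90% power. That is not shown. The H72 contrast keeps 90%, and the change test, or the interaction with a D8 difference of 0 or 4, reaches 90% at a correlation of about 0.5.
- A reader might infer that a true H72 effect could appear with the wrong sign. With differences (0, 4, 0), a straight-line slope is indeed 4 × (−0.0204) = −0.08 per day. But this needs a linear time term and full convergence of citrulline by D8, and the plan states neither. A mixed linear model is a class of model, not a coding of time. Convergence of the feeding routes does not show that citrulline levels have converged.

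The caution about D0 adjustment also stands. The footnote to the 4.2.7 flowchart runs D0 from inclusion to 11:59 pm, so a D0 sample could be drawn after study feeding has begun. Adjustment is safe only for a value drawn before that.

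**Conclusion.** The point holds as a mismatch and an under-specification. The outcome and the 85 per group concern one difference at H72; the primary analysis is referred to a method that does not name it. Power is 90% if the H72 contrast is used. Among the alternatives that the wording allows, it runs from well below 90% to above it. The lowest figures, 17% to 35%, belong to one possible coding (linear time) with an assumed D8 difference of 2, and should not be read as the expected result. All figures other than the H72 contrast rest on the assumed correlations, and those that use D8 rest also on the assumed D8 difference.

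This should be corrected, but its reach is limited to a 170-patient ancillary study. The main mortality comparison is unaffected.

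**What to change.** In 7.1.5, replace the cross-reference. State the primary analysis as the between-group difference in H72 citrulline from a linear model with group and D0 citrulline as terms, transformed if needed, and say that the D3 sample supplies the H72 value. Specify that the D0 value must have been drawn before study feeding starts; if that cannot be assured, use the unadjusted H72 contrast, which keeps the planned 90%. Keep the D0/D3/D8 mixed model as the secondary analysis.

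In 7.2, state that the 90% power refers to 85 patients per group with an H72 value, and give the power for the loss expected.

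The cost is wording, plus a check of D0 sampling times against the start of feeding. D0 citrulline is already collected, and sample collection times are already recorded under 4.6. The change should be dated before any comparison of citrulline by group.

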#### 4.2.7 Patient follow-up

The following will be recorded until the patient is extubated: vital signs, nutrition monitoring data, laboratory tests, and data relevant to nosocomial infections. The patient will

be followed-up to hospital discharge, D28, and D90. At these time points, vital status will be recorded. Below is a flowchart of patient follow-up.

	Inclu-sion	Rando-mization	D0*	D1 to Dn	End of study	D28	D90
Eligibility: check inclusion and exclusion criteria	X						
Patient information and consent	X						
Randomization	X						
Demographics	X						
Characteristics			X				
Ventilation			X				
Laboratory tests			X	X*			
SOFA			X	X			
Nutritional evaluation			X	X			
Treatments used			X	X			
Daily calorie intake				X			
Nosocomial infections					X		
Final extubation						X	
Final discontinuation of nutritional support						X	
Survived / died					X	X	X

\*from time at inclusion to 11:59 pm

---

Design of the ancillary studies

---

### Ancillary study 1

The plasma citrulline and I-FABP assays on D0, D3, and D8 will be performed using blood drawn as part of the standard care of critically ill patients; the volume of each blood sample will be increased slightly (by about 2 mL) to allow these assays. For amino acid chromatography, blood will be drawn in a lithium heparin tube, which will be transported on ice as promptly as possible to the medical biochemistry laboratory. At arrival at the laboratory and within 2 hours after blood collection, the sample will be centrifuged (4°C, 1900 rpm, 10 minutes) and the plasma stored at -70 °C until the analysis.

The samples will be centralized at the Biology Center of the Besançon Teaching Hospital. After thawing and deproteinization, ion-exchange chromatography will be performed on a Hitachi L-8800 analyzer (Hitachi, Tokyo, Japan).

I-FABP will be assayed using a blood sample drawn into an EDTA tube, which will be taken as rapidly as possible to the medical biochemistry laboratory. At arrival at the laboratory, the sample will be centrifuged (4°C, 1500 rpm, 15 minutes) and the plasma stored at -70°C until analysis by ELISA (Hycult Biotech, Uden, The Netherlands) at the Biology Center of the Besançon Teaching Hospital.

### Ancillary study 2

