#### Additional data collected during the ancillary studies

##### – Ancillary study 1

Plasma citrulline and I-FABP assays on D0, D3, and D8. Blood will be drawn by the nurse in charge of the patient as part of standard care. Each blood sample will be labeled with the number assigned to the patient, the first initial of the patient's last and first names, the patient's date of birth, the date and time of sample collection, and the number assigned to the sample.

For amino acid chromatography, the blood samples will be centrifuged within 2 hours after collection (4°C, 1900 rpm, 10 minutes) and the plasma stored at -70 °C at the study center.

For the I-FABP assay, the blood samples will be centrifuged (4°C, 1500 rpm, 15 minutes) and the plasma stored at -70°C until the analysis.

An accredited transporter will take the samples to the Biology Center of the Besançon Teaching Hospital, where they will be processed. The samples will be destroyed after the assays are performed.

##### – Ancillary study 2

D0, D3, and D8: pepsin and salivary amylase assays in all tracheal aspirates

The tracheal aspirate samples will be collected by the nurse in charge of the patient, according to standard practice. Each sample will be labeled with the number assigned to the patient, the first initial of the patient's last and first names, the patient's date of birth, the date and time of sample collection, and the number assigned to the sample. Each tracheal aspirate sample (about 1-2 mL per aspirate) will be stored at -20 °C at the biochemistry department of each

study center. An accredited transporter will take the samples to the Biology and Pathology Center of the Lille Teaching Hospital, under the responsibility of [name], [name], and [name], for blinded assays of pepsin and salivary amylase. Pepsin levels will be measured using an ELISA, under the responsibility of [name] and [name], at the Molecular Biochemistry-Biology Laboratory headed by Pr. [name], Biochemistry Department, Lille Teaching Hospital. The amylase assays will be performed under the responsibility of [name] at the Biochemistry, Proteins, and Predictive Biology Laboratory headed by Pr [name], Biochemistry Department, Lille Teaching Hospital. A colorimetric enzyme assay will be used. The level of salivary amylase will be computed as the difference between total and pancreatic amylase levels. The samples will be destroyed after the assays are performed.

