#### 7.1.1 Description of the groups at baseline

The groups established by randomization will be compared using descriptive statistics. No statistical tests will be performed.

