#### 7.1.3 Analysis of the primary endpoint

Day-28 mortality will be reported as the point estimate with the 95% confidence interval in each group. Day-28 mortality will be compared between the two groups using the chi-square test.

---

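### Ancillary study 1 tests inclusion-day (D0) threshold proportions between groups, and its D3 and D8 threshold tests leave out the D0 level already collected

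*Combined protocol and SAP*

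**What the plan says.** Section 4.1.3 lists the I-FABP and citrulline threshold proportions on D0, D3 and D8 among the secondary outcomes of ancillary study 1. Section 7.1.5 gives their analysis. For I-FABP it reads "pg/mL on D0, D3, and D8: the analysis method will be the same as for the primary NUTRIREA2 outcome measure"; for citrulline, "L/L on D0, D3, and D8: the analysis method will be the same as for the primary NUTRIREA2 outcome measure".

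The method referred to is in section 7.1.3: "Day-28 mortality will be compared between the two groups using the chi-square test". It has no covariate.

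For baseline, section 7.1.1 says that the randomised groups will be compared descriptively and adds: "No statistical tests will be performed".

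The follow-up chart in section 4.2.7 defines D0 as "from time at inclusion to 11:59 pm". The D0 values exist by design: section 4.6 schedules "Plasma citrulline and I-FABP assays on D0, D3, and D8".

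The continuous levels of both markers at D0, D3 and D8 are handled differently in section 7.1.5: "For between-group comparisons, a mixed linear model will be built, after transformation of the data if needed". The plan does not say whether D0 enters that model as a covariate, a constrained baseline or a free response.

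**The concern.** A marker measured on the day of inclusion is a baseline or near-baseline value. If the blood was drawn before the allocated feed, randomisation guarantees that any group difference at D0 is chance, so a test of it answers no question about enteral versus parenteral feeding. The plan still treats D0 as an outcome to be tested, twice, with no multiplicity rule.

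At D3 and D8 the same D0 measurement would be useful as a covariate, because patients enter in shock and some may already be past a threshold. The unadjusted chi-square does not use it. At stake are two avoidable tests and some lost power on secondary endpoints of a 170-patient ancillary study. Neither day-28 mortality nor the ancillary primary outcome (citrulline at H72) is affected.

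**Working it through.** **Inputs from the plan.** Section 7.2, ancillary study 1: citrulline 16 vs 12 µmol/L, SD 8, two-sided alpha 0.05, power 90%, 85 per group. Section 7.3: final threshold 4.9%. Section 4.1.3: threshold proportions on D0, D3 and D8.

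**Inputs assumed.** The D0–D3 correlation is not given; 0.3, 0.5 and 0.7 are used. Levels are taken as normal and H72 as D3. The citrulline cut-off of 10 is printed in µL/L; it is read here as µmol/L, the unit of the sample-size section.

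**1. Reproduce the plan's figure.** n = 2 × (1.960 + 1.282)² × 8² / 4² = 84.1, rounded up to 85 per group. This matches; power at 85 is 90.3%.

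**2. Chance findings from the D0 tests.** For k independent tests, the chance of at least one false positive is 1 − (1 − α)^k.
- Two D0 tests: 1 − 0.95² = 9.75%; at 4.9%, 1 − 0.951² = 9.56%.
- All six threshold tests: 1 − 0.95⁶ = 26.5%.
- The four D3 and D8 tests alone: 1 − 0.95⁴ = 18.5%.

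Simulation with correlation 0 to 0.7 between days within a marker, and independent markers, gave 24–26% for six tests and 17–18% for four. If the two markers were fully dependent, the D0 figure would fall to 5%.

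**3. Size of a chance D0 difference.** With 85 per group, 1.96 × √(2p(1 − p)/85) is 9.0 percentage points at an assumed p = 10% and 15.0 at p = 50%. One null comparison in twenty exceeds this.

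**4. Cost of leaving D0 out at D3.** The plan's means and SD imply these proportions at or below 10:
- enteral: Φ((10 − 16)/8) = Φ(−0.75) = 22.7%;
- parenteral: Φ((10 − 12)/8) = Φ(−0.25) = 40.1%.

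The formula power of the chi-square test at 85 per group is 69.2%. In 2,000 simulated trials per correlation, with D0 levels centred at 14 in both groups, the unadjusted test was compared with logistic regression including the D0 level:

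| Assumed correlation | Chi-square power | Adjusted power | Gain (points) | Type I error, unadjusted / adjusted |
|---|---|---|---|---|
| 0.3 | 68.3% | 70.8% | 2.5 | 5.4% / 5.4% |
| 0.5 | 70.5% | 76.4% | 5.9 | 5.1% / 5.1% |
| 0.7 | 71.3% | 84.9% | 13.7 | 4.4% / 4.8% |

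The spread in the chi-square column is simulation noise, since that test does not depend on the correlation. The simulation used the untransformed D0 level and assumed that every patient has a usable one; each unusable value reduces the gain. I-FABP could not be treated this way because the plan gives no mean or SD for it.

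**The case against.** Five points can be made for the plan.

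- **The D3 and D8 tests are valid.** This stands. A reader might infer that ignoring D0 lets chance imbalance contaminate the later comparisons. In the few simulated null trials with a significant D0 difference (90 to 107 of 2,000), the unadjusted D3 test did reject more often, at 7% to 12%. But its alpha already covers that variation: over all trials its error was 4.4% to 5.4%. The cost is precision.
- **D0 is not ignored.** This stands for the continuous levels, which enter a mixed model. A reader might infer that the baseline measurement is wasted altogether; section 7.1.5 does not support that.
- **A D0 difference need not be chance.** This stands in part. The D0 window runs to midnight, section 4.2.3 has feeding start as soon as possible, and blood comes from routine draws. Some D0 samples may follow the feed. For those, a difference could reflect treatment, and adjusting for the value would condition on something measured after treatment began. The fix has to allow for this.
- **Section 7.1.1 does not name the ancillary outcomes.** This stands. Section 7.1.5 also plans tests on patient characteristics in ancillary study 2, which suggests that the authors did not take 7.1.1 to bind those studies. The conflict is one of principle, so a reader should not call it a direct textual contradiction.
- **Gains quoted on the continuous scale do not apply.** This stands. A correlation ρ removes ρ² of the variance of a continuous outcome (9% at 0.3, 49% at 0.7), but the analysis here is of a yes/no endpoint. Only the simulated power gains should be used.

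**Conclusion.** The point holds in limited form. Two tests of an inclusion-day value are planned as outcome comparisons. For samples drawn before the feed they cannot inform about feeding route, and they add about a 10% chance of a spurious result if the markers are independent (5% if fully dependent).

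The unadjusted D3 and D8 tests are sound but less precise than the collected data allow: about 2.5 to 14 points of power for citrulline at or below 10. That range rests on assumed correlations of 0.3 to 0.7, normal levels, the plan's own 16 vs 12 with SD 8, and a usable D0 value for everyone.

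The consequence is small. These are dichotomised secondary endpoints of an ancillary study, and the change is an improvement to the plan; it does not repair an invalid analysis.

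**What to change.** In section 7.1.5, for the two threshold endpoints of ancillary study 1:

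- Report the D0 proportions by group descriptively, without a test.
- Compare the D3 and D8 proportions by logistic regression including the patient's own D0 level on the log scale. State how undetectable I-FABP values enter.
- Use D0 as a covariate only when the recorded sample time precedes the allocated feed. Treat other D0 values as missing baseline, for example with a missing indicator, and tabulate the share of usable D0 values by group. The indicator is safe only if that share does not depend on allocation.
- Report the raw D3 and D8 proportions beside the adjusted result.

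Sample labels already carry the time of collection (section 4.6). The time at which feeding started is not named in the section 4.6 data list, so it may have to be taken from the bedside nutrition charts.

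The cost is plan wording and a little data work, with no change to site sampling. Section 7.6 leaves the analysis plan open until database lock. The downsides are that the effect becomes a conditional odds ratio, which is why the raw proportions should stay in the report, and that some D0 values may be unusable, which reduces the gain.
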